1. OVERALL SYNOPSIS OF THE CLINICAL INVESTIGATION

Clinical investigation title:	Calibration and Validation of the Masimo Rad-G with Temperature device in Febrile Patients
Study objective(s):	The objective of this study is to gather temperature data using the Masimo Rad-G with Temperature for calibration and validation purposes.
Investigational device(s):	Masimo Rad-G with Temperature
Number of participants:	Up to 250 participants.
Inclusion criteria:	
Participant age \geq 1 year oldFebrile at time of enrollment: \geq 99.5°F/37.5°C for sublingual temperature reference; \geq 100.4°F/38°C for temporal artery temperature reference.English- or Spanish-speaking patient or parent/Legally Authorized Representative (LAR)
Exclusion criteria:	
Participants deemed not suitable for the study at the discretion of the investigatorPatients who are rated as a 1 or 2 Emergency Severity Index
Duration of the clinical investigation:	The expected duration of study enrollment is 1 to 3 months.
Study endpoint(s):	For the validation phase of the study, accuracy of temperature measurements using the Masimo Rad-G with Temperature will be compared to reference temperature measurements.

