6. DESIGN OF THE CLINICAL INVESTIGATION

6.1. General

This is a prospective, nonrandomized, single arm study. Temperature data will be obtained using the Masimo Rad-G with Temperature while obtaining [REDACTED]

There will be up to 250 participants enrolled into this study, divided into two groups: calibration and validation. [REDACTED]

[REDACTED] The second group will be the validation set that will be used to evaluate study objectives.

[REDACTED] For the validation phase of the study, accuracy of temperature measurements using the Masimo Rad-G with Temperature will be compared to [REDACTED]

The validation of the accuracy of the temperature measurement in the investigational device may be determined using data collected from this study, in addition to data from other Masimo sponsored studies.

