6.2. Equipment and Materials

Equipment and materials are to be used as required. All study personnel will be trained on the use of relevant equipment.

Investigational Device

- Masimo Rad-G with Temperature

Reference Equipment (as needed)

- Hospital standard of care [REDACTED] thermometer
- Hospital grade [REDACTED] thermometer

Research Equipment

- Laptop with data collection software

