6.4. Participants

Inclusion Criteria

- Patients age \geq 1 year old
- Febrile at time of enrollment: $\geq 99.5^{\circ}\text{F}/37.5^{\circ}\text{C}$ for sublingual temperature reference; $\geq 100.4^{\circ}\text{F}/38^{\circ}\text{C}$ for temporal artery temperature reference.
- English- or Spanish-speaking patient or parent/LAR

Exclusion Criteria

- Patients deemed not suitable for the study at the discretion of the investigator
- Patients who are rated as a 1 or 2 Emergency Severity Index

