6.5.3. Data Collection Procedure

6.5.3.1. Data collected by the Rad-G with Temperature is not intended to be used for clinical decisions, and research personnel should continue to use standard of care procedures for monitoring participants.

6.5.3.2. Study duration will be approximately 15 to 30 minutes.

6.5.3.6. Record start and end time of data collection procedures on the CRF.

6.5.3.7. Take the screening temperature measurement using the same thermometer to be used for the reference measurements, immediately before beginning the study measurements. The subject should be withdrawn from the study if they do not meet the criteria for temperature [REDACTED]

Reference Measurements

Multiple reference measurements may be obtained.

6.5.3.12. The three measurements need to be taken in quick succession of each other, with approximately 3 seconds between each measurement

6.5.3.13. Be sure to keep the Rad-G device steady during the measurement.

6.5.3.15. In the validation phase, [REDACTED] measurements will be obtained per subject.

6.5.3.16. Data from the Rad-G with Temperature device will be downloaded using Masimo [REDACTED] software on the data collection laptop at the end of each day. Reference data [REDACTED] will be downloaded to the data collection laptop using a USB flash drive.

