7. STATISTICAL DESIGN AND ANALYSIS

7.1. Acceptance Criteria

7.3. Sample Size

The [REDACTED] minimum of 32 febrile patients for the validation phase per ISO 80601-2-56:2017, section 201.102.

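### Does allowing either a sublingual or a temporal artery reference leave the validation accuracy dependent on the mix of thermometers?

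*Combined protocol and SAP*

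**What the plan says.** The synopsis (Section 1) and Section 6.4 make the definition of fever depend on the reference: "99.5°F/37.5°C for sublingual temperature reference" or "100.4°F/38°C for temporal artery temperature reference". Section 6.2 lists two reference thermometers for use where needed, with the types blacked out. Section 6.5.3 requires the screening reading to be taken "using the same thermometer to be used for the reference measurements", so the threshold a subject must meet follows from that subject's reference.

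The synopsis endpoint for validation is that "accuracy of temperature measurements using the Masimo Rad-G with Temperature will be compared to reference temperature measurements", with no division by reference type. Section 7.3 gives a "minimum of 32 febrile patients for the validation phase per ISO 80601-2-56:2017, section 201.102", and 7.4 adopts the procedure of the same ISO section. Section 6.1 adds that the validation of accuracy "may be determined using data collected from this study, in addition to data from other Masimo sponsored studies".

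Much of the neighbouring text is withheld. The comparator wording in 5, 6.1 and 6.3 is cut. So is the temperature-withdrawal rule in 6.5.3, where steps 6.5.3.8 to 6.5.3.11 and 6.5.3.14 do not appear. Section 7.1 has a heading only, 7.2 is absent, and there is a redaction in 7.3 just before the minimum of 32.

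**The concern.** The endpoint is the device reading minus the reference reading, so the choice of reference is part of what is estimated. If device error against a temporal artery thermometer differs from device error against a sublingual one, a single combined mean is the error against neither. The difference also adds to the spread. The reported accuracy would then depend partly on how many subjects had each thermometer, and the readable text does not fix that number. Data from other sponsor studies could shift the mix further. In the worst arrangement, equal and opposite errors against the two references in an even mix would average to zero and hide both. Section 17 says that validation results will be made public, so a reader needs to know which reference a figure refers to.

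**Working it through.** **The plan's own figures.** The paired thresholds agree: (99.5 − 32)/1.8 = 37.5 °C and (100.4 − 32)/1.8 = 38.0 °C. The minimum of 32 is taken from the ISO standard. The readable text gives no alpha, power, SD or accuracy limit, so the figure can be neither reproduced nor called wrong.

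**Inputs for the mixing effect.** Three quantities are needed, and the documents give none of them:
- d, the difference in device error between references: assumed 0 to 0.5 °C
- p, the share of subjects with a temporal artery reference: assumed 0.25, 0.5 or 0.75
- s, the SD within a reference: assumed 0.20 to 0.40 °C, equal for both

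The 0.5 °C gap between entry thresholds is not a stated measurement offset. It serves only as the top of the illustrative range.

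**Formulae.** Shift of the combined mean from the sublingual figure = p·d. Combined SD = √(s² + p(1 − p)d²). 95% limits half-width = 1.96 × SD.

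**Results for s = 0.30, p = 0.5:**

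| d (°C) | Mean shift (°C) | SD (°C) | Half-width (°C) | Widening |
|---|---|---|---|---|
| 0 | 0 | 0.300 | 0.588 | 0% |
| 0.1 | 0.05 | 0.304 | 0.596 | 1.4% |
| 0.25 | 0.125 | 0.325 | 0.637 | 8.3% |
| 0.5 | 0.25 | 0.391 | 0.765 | 30% |

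For example, at d = 0.25 the SD is √(0.0900 + 0.25 × 0.0625) = √0.105625 = 0.325.

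At p = 0.25 or 0.75 the half-widths are 0.588, 0.594, 0.625 and 0.725 °C. Moving p from 0.25 to 0.75 moves the combined mean by 0.5·d, which is 0.25 °C at d = 0.5. At p = 0.5, going from d = 0 to d = 0.5 takes the half-width from 0.392 to 0.628 °C if s = 0.20, and from 0.784 to 0.925 °C if s = 0.40.

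**What splitting would cost.** The 95% CI half-width for a mean error is t(0.975, n − 1)/√n in SD units: 0.361 at n = 32, 0.422 at n = 24, 0.533 at n = 16 and 0.836 at n = 8. A 24/8 split would leave the smaller group with an interval about 2.3 times as wide as that from all 32 (0.836/0.361).

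**Is the condition met?** The arithmetic applies only if both references occur in the validation set and are summarised together.
- The inclusion criteria cover the whole study, calibration included. One thermometer could serve calibration only, and the readable text does not rule this out.
- The sentences that would name the validation comparator are the ones cut in 5, 6.1 and 6.3.
- The analysis is specified by citation. Whether the ISO procedure deals with reference type cannot be seen from the documents.

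The readable text therefore neither establishes the condition nor excludes it.

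**Can the split be made later?** Yes. Eligibility is judged on a threshold specific to the reference, with the same thermometer used for the reference readings, so the site must know which one each subject had.

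**The case for a change.** The best case for a change is that the algebra needs no outside source, both references are named without restriction to calibration, and no readable sentence promises results by reference. One sentence in 7.4 and one extra table would settle the matter, and a combined figure could still be shown. If the references agree, the split table shows it. If they do not, it prevents a headline figure that depends on thermometer allocation.

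The quotations and the arithmetic stand, and the table would be cheap. What does not stand is the step from silence in the readable text to a fault in the plan. Redacted text is not missing text, and the redactions fall where this point would be settled. At most, the mix is not described in what can be read; it cannot be called unplanned.

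The size is not shown either. The widening runs from 0% to 30% depending wholly on assumed values. Any cut-off for importance needs an accuracy limit, and 7.1 is withheld.

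Nor would a split isolate the thermometer. The two groups enter at different temperatures and no random assignment of reference is described, so a difference between them could also reflect fever range or type of patient. The model is simplified as well: it takes one reference per subject and equal SDs, while 6.5.3 allows several reference measurements.

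**Conclusion.** No change to the plan follows. Two references with different entry thresholds are allowed, and the readable text does not say which is used in validation or whether accuracy is shown by type. That is missing detail in a heavily redacted document; no stated rule is shown to give a wrong result.

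If both references do enter validation and are pooled, the effect is small at a difference of 0.1 °C (1.4% wider limits) and reaches 30% at 0.5 °C, with s = 0.30 °C and an even mix. All three inputs are assumed. If the references agree, or only one is used, the effect is nil.

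The sponsor can be asked to confirm which reference or references are used in validation, how a subject's reference is chosen, and whether 32 is a total or a number per reference. If both are used, an analyst would sensibly show mean error and spread by reference, with the counts, beside any combined figure. Those intervals would be wider, and a difference between the groups would not be evidence about the thermometer alone.

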2. IDENTIFICATION AND DESCRIPTION OF THE INVESTIGATIONAL DEVICE

Masimo Corporation is the developer of noninvasive technologies for the measurement and monitoring of physiological variables, such as arterial oxygen saturation (SpO₂), total hemoglobin concentration (SpHb), carboxyhemoglobin concentration (SpCO), methemoglobin concentration (SpMet), and other physiological variables to improve patient outcomes and reduce cost of care.

The Masimo Rad-G with Temperature device (see Figure 1) is a non-contact infrared thermometry device. Non-contact infrared thermometers utilize infrared sensors that detect thermal radiation from the body.

The device is a non-invasive, non-contact, handheld pulse oximetry device with a rechargeable battery and LCD display. It uses Masimo Measure-through Motion and Low Perfusion™ SET® pulse oximetry technology to measure SpO₂, respiration rate from the Pleth (RRp™), pulse rate (PR), perfusion index (PI), and temperature. The Masimo Rad-G is not FDA cleared and is considered investigational. Though the Rad-G may be used to measure the aforementioned parameters, the Rad-G used in this study will only be used to measure body temperature.

Figure 1: Masimo Rad-G with Temperature with integrated infrared temperature sensor at back of the device

3. JUSTIFICATION FOR THE DESIGN OF THE CLINICAL INVESTIGATION

This study is designed to be a two-phase calibration and validation study to obtain data for product development and clinical performance of the Masimo Rad-G with Temperature. [REDACTED]

[REDACTED] The second phase of the study will be the validation phase and will be used to evaluate the accuracy of temperature measurements using the Masimo Rad-G with Temperature.

4. BENEFITS AND RISKS OF THE INVESTIGATIONAL DEVICE, CLINICAL PROCEDURE, AND CLINICAL INVESTIGATION

4.1. Anticipated Benefits

There will be no direct benefits to the enrolled participants; however, this study hopes to learn more about the temperature device to potentially help other patients in the future. Other possible benefits would be to society as a whole.

4.2. Risks/Discomforts Associated with Participation in the Clinical Investigation

The Rad-G with Temperature device does not pose risks to the participant, because the device is non-contact and does not emit any energy. [REDACTED] using normal practice.

The other main risk associated with the study is a potential breach of confidentiality which will be minimized by limiting the collection of protected health information (PHI) and through secure data storage practices. None of our measures are diagnostic in nature. There is no other foreseeable risk associated with this study.

4.3 Importance of Knowledge Gained

Development of new temperature technologies could enable users to monitor temperature vital signs remotely and lessen the need for hospital visits.

5. OBJECTIVES OF THE CLINICAL INVESTIGATION

The objective of this study is to collect data for the calibration and validation of the Masimo Rad-G with Temperature to evaluate the performance of the device in obtaining temperature measurements. Measurements from the Masimo Rad-G with Temperature will be compared to [REDACTED]

6. DESIGN OF THE CLINICAL INVESTIGATION

6.1. General

This is a prospective, nonrandomized, single arm study. Temperature data will be obtained using the Masimo Rad-G with Temperature while obtaining [REDACTED]

There will be up to 250 participants enrolled into this study, divided into two groups: calibration and validation. [REDACTED]

[REDACTED] The second group will be the validation set that will be used to evaluate study objectives.

[REDACTED] For the validation phase of the study, accuracy of temperature measurements using the Masimo Rad-G with Temperature will be compared to [REDACTED]

The validation of the accuracy of the temperature measurement in the investigational device may be determined using data collected from this study, in addition to data from other Masimo sponsored studies.

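### Does the option in section 6.1 to add data from other sponsor studies leave open which data set decides the accuracy result?

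*Combined protocol and SAP*

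**What the plan says.** Section 6.1 (General) describes up to 250 participants "divided into two groups: calibration and validation". It then gives the second group its purpose: "The second group will be the validation set that will be used to evaluate study objectives". The section closes with a separate statement that validation of the temperature accuracy of the investigational device "may be determined using data collected from this study, in addition to data from other Masimo sponsored studies". The other studies are not identified.

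Other sections bear on the same point:

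- **Section 1 (Synopsis), endpoint:** "For the validation phase of the study, accuracy of temperature measurements using the Masimo Rad-G with Temperature" is to be compared with reference temperatures. Outside data are not mentioned.
- **Section 3:** the second phase "will be the validation phase and will be used to evaluate the accuracy of temperature measurements".
- **Section 5:** the aim is to collect data for calibrating and validating the device, "to evaluate the performance of the device in obtaining temperature measurements".
- **Section 6.4:** every participant must be "Febrile at time of enrollment".
- **Section 7.3:** a "minimum of 32 febrile patients for the validation phase per ISO 80601-2-56:2017, section 201.102".
- **Section 7.4:** the analysis follows the procedure in the same clause of the ISO standard.
- **Section 17:** the validation-phase results are to be made public.

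Section 7.1 (Acceptance Criteria) shows only its heading, section 7.2 is not visible, and parts of 6.1 and 7.3 are blacked out.

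**The concern.** Two statements in one section appear to assign the accuracy question to different data: first to this study's validation group, then, as an option, to that group plus unnamed studies. The option carries no visible selection rule, combination method or timing. Section 5 also states the study's own aim in terms of device performance, so the study endpoint and the validation of the device are not cleanly separated in wording.

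If the pooled result decided the endpoint, a mean error in febrile patients could be averaged down by outside subjects with smaller errors. If the sponsor could also choose between the stand-alone and the pooled result after seeing both, the chance of a false pass would rise. Participants used for calibration in another study might enter the pooled set as well. Within this study the two groups are already separate.

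**Working it through.** **1. Which data set does the visible text assign to which question?**

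| Question | Where | Data named |
|---|---|---|
| Study objectives | 6.1, second group | This study's validation group |
| Accuracy endpoint | Synopsis; section 3 | This study's validation phase |
| Minimum sample size | 7.3 | This study's validation phase, 32 febrile patients |
| Public results | 17 | This study's validation phase |
| Validation of the device's temperature accuracy | 6.1, last sentence | This study, optionally with other sponsor studies |

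The first four rows agree. Only the last admits outside data. Its subject is the device, and it mentions neither the objectives, nor the endpoint, nor an acceptance criterion. The rows can all be true together: the study is judged on its own validation group, and its data may later join a larger body of evidence on the device. Section 5 fits this, because it describes the study as collecting data for calibration and validation. So does section 6.4, because a febrile-only cohort cannot by itself show accuracy at normal temperatures.

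**2. How large could dilution be if a pooled mean did decide?**

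The plan gives no figure to reproduce. The inputs from the documents are n = 32 (section 7.3) and the ceiling of 250 (section 6.1). Everything else is assumed: m outside subjects, a subject-weighted mean, and r, the ratio of the outside mean error to the febrile group's mean error.

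Weight of the validation group: w = n/(n + m). Share of its mean error seen in the pooled mean: w + r(1 − w).

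| n = 32 | m = 32 | m = 64 | m = 128 |
|---|---|---|---|
| w | 32/64 = 0.500 | 32/96 = 0.333 | 32/160 = 0.200 |
| share, r = 0 | 0.500 | 0.333 | 0.200 |
| share, r = 0.5 | 0.750 | 0.667 | 0.600 |
| share, r = 1 | 1 | 1 | 1 |
| share, r = 2 | 1.500 | 1.667 | 1.800 |

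With n = 125 (assumed, half of 250, as the split is not visible), w = 125/157 = 0.796, 125/189 = 0.661 and 125/253 = 0.494.

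Pooling therefore helps or hurts the device according to r, on which the documents are silent. A larger outside error of the same sign (r above 1) makes the pooled result worse.

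**3. What would a free choice between two results cost?**

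Assume a one-sided test at 0.025, equal variances and no true difference from the null. The stand-alone and pooled statistics then have correlation √(32/(32 + m)), which is 0.707, 0.577 and 0.447 for m = 32, 64 and 128. The chance that at least one passes is 0.0416, 0.0442 and 0.0461, with an upper bound of 1 − 0.975² = 0.0494. No visible text contains such a test or grants such a choice, so these figures show direction only.

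**4. What does pooling offer?**

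If bias and SD were equal across studies, the standard error for 32 alone against 32 plus 64 would be √(96/32) = 1.73 times larger. Combining data for a device-level question has a legitimate purpose.

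**The case for a change.** The strongest case for a change is that the wording is permissive and unanchored. It leaves open whether outside data are used, from which studies, and when that is decided. Section 7.4's visible text does not mention pooling. The exclusions in 7.4.1 concern participants and do not help select studies. The bibliography identifies no outside study. Section 17 makes the validation-phase results public without saying that they alone decide. One clarifying sentence would need no new patients or measurements.

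Part of this stands. The last sentence of 6.1 is loose, and it does not point to any section where a rule might be found. But the case goes from loose wording to a defect in two steps that the documents do not support. The first treats the absence of a visible rule as the absence of a rule, although acceptance criteria have their own section, whose body is not visible, and 6.1 is itself partly blacked out. The second supposes that a single pooled mean decides the endpoint, which no visible passage says. Making every combined analysis supplementary would also rank analyses in a device programme that reaches beyond this protocol.

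**Conclusion.** The concern does not call for a change. An analyst following the visible plan would evaluate the endpoint in this study's validation group and would treat any combination with other studies as evidence on the device more widely. That conclusion is sound as it stands. What remains is a minor ambiguity of wording that the neighbouring text resolves.

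No bias, inflated error rate or wrong result can be shown from the documents. The weights of 50%, 33% and 20% are correct arithmetic, but they rest on assumed outside sample sizes and on an assumed pooled mean.

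This judgement rests on reading the closing sentence of 6.1 as being about the device, and on the text that is not visible in 6.1 and 7.1 to 7.3 not saying otherwise. If that text made a pooled result decisive for this study's endpoint without fixing the studies in advance, the question would have to be reopened.

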6.2. Equipment and Materials

Equipment and materials are to be used as required. All study personnel will be trained on the use of relevant equipment.

Investigational Device

- Masimo Rad-G with Temperature

Reference Equipment (as needed)

- Hospital standard of care [REDACTED] thermometer
- Hospital grade [REDACTED] thermometer

Research Equipment

- Laptop with data collection software

